3.3 Randomization and blinding

Eligible subjects will be randomized in a 2:1 fashion to either reparixin or standard of care through an Interactive Response System (IRS).

Randomization will be stratified by site to ensure balanced assignment across treatment groups. A stratified permuted block randomization list will be generated with a computer procedure, randomizing an excess of subjects to allow competitive recruitment within each center. Each randomized subject will be allocated with randomization number according to the stratified randomization list.

Given the open-label nature of the trial and the stratification by site, random block sizes will be adopted in the randomization list to avoid that treatment assignments might be forecasted by investigators.

The master randomization list will be kept confidential and will not be disclosed to any other person than those for which is strictly required (i.e. independent statistician who create the list, and IRS provider personnel).

Mis-randomization events will be recorded as major deviation and reported in the final study report.

Randomization codes will not be reused in case of subject's dropouts.

3.4 Overview of planned statistical analyses

The study plans for the following statistical analyses:

- Phase 2:
 - Interim analysis for efficacy or futility: this analysis will be conducted by Data Monitoring Committee (DMC) when half of the planned events of primary endpoint of phase 2 has happened;

- Final analysis: this analysis will be conducted when all randomized phase 2 subjects has performed the final visit.
- Phase 3 (in case of success of phase 2):
 - Interim analyses for efficacy or futility: this analysis will be conducted by DMC when approximately 55% and 74% of the planned severe events of primary endpoint of phase 3 has happened;
 - Final analysis: this analysis will be conducted all randomized phase 3 subjects has performed the final visit.
- Analyses for the DMC: these analyses will be produced periodically according to the DMC charter. In addition to the above interim analyses, analyses for safety integrity reviews will be performed according to DMC charter.

3.5 Efficacy endpoints

3.5.1 Primary endpoints

- Primary Endpoint for phase 2: Composite endpoint of clinical events (the subject requires at least one of the following: supplemental oxygen requirement, invasive mechanical ventilation use, admission to ICU, and use of a rescue medication for any reason);
- Primary Endpoint for phase 3: Composite endpoint of death and clinical severe events (the subject dies or requires invasive mechanical ventilation use and/or admission to ICU).

3.5.2 Secondary Endpoints:

- Clinical severity score (a seven-category ordinal scale) at any available time point
- Dyspnea severity (Liker categorical scale and VAS continuous scale) at any available time point;
- Changes in body temperature at any available time point;
- Duration and quantity of supplemental oxygen treatment at any available time point;
- Incidence and duration of mechanical ventilation use at any available time point;
- Incidence of ICU admission need at any available time point;
- Lung damage extension changes from baseline (assessed by Chest CT or Rx) at any available time point;
- Change from baseline in lung exudation degree (assessed by Chest CT or Rx) at any available time point;
- PaO₂ at any available time point;
- SpO₂ at any available time point;
- Partial arteriolar oxygen pressure (PaO₂) to fraction of inspiration O₂ (FiO₂) ratio at any available time point;
- CRP at any available time point;
- Hs-CRP at any available time point;

3.5.3 Exploratory Endpoints (not mandatory):

- Cytokine profile at any available time point;

- Concentration of reparixin in serum over time;
- SARS-CoV-2 virologic counts at any available time point.

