### - Phase 2/3 Study Endpoints:

- **Primary Endpoint for Phase 2:** Composite endpoint of clinical events (the patient requires at least one of the following: supplemental oxygen requirement, mechanical ventilation use, admission to ICU, and use of a rescue medication for any reason)
- **Primary Endpoint for Phase 3:** Composite endpoint of death and clinical severe events (the patient dies or requires mechanical ventilation use and/or admission to ICU)
- Secondary Endpoints:
  - Changes in clinical severity score (as recommended by WHO for COVID studies), defined as the time to clinical improvement of two points from the time of randomization on a seven-category ordinal scale or live discharge from the hospital, whichever comes first. The seven-category ordinal scale consists of the following: 1) not hospitalized, with resumption of normal activities; 2) not hospitalized, but unable to resume normal activities; 3) hospitalized, not requiring supplemental oxygen; 4) hospitalized, requiring supplemental oxygen; 5) hospitalized, requiring high-flow oxygen therapy, noninvasive mechanical ventilation, or both; 6) hospitalized, requiring ECMO, invasive mechanical ventilation, or both; and 7) death.
  - Dyspnea severity (Liker scale and VAS scale)
  - Changes in body temperature
  - Changes hematology test values
  - o Duration and quantity of supplemental oxygen treatment
  - Incidence and duration of mechanical ventilation use
  - o Incidence of intensive care unit (ICU) admission need
  - Lung damage extension changes from baseline (assessed by Chest CT or Rx)
  - Change from baseline in lung exudation degree (assessed by Chest CT or Rx)
  - o PaO2
  - o SpO2
  - Partial arterioral oxygen pressure (PaO2) to fraction of inspiration O2 (FiO2) ratio
  - o CRP
  - o Hs-CRP

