4.9 Changes in the planned analysis

No change has been implemented in this SAP.

However, in order to clarify the analysis of the primary endpoint, a clarification of the meaning of "supplemental oxygen treatment" is provided: since all patients enrolled in this study had a respiratory distress, it is intended in all the analysis that the term "supplemental" refers to additional and/or increased oxygen requirement as compared to the baseline. In fact, all patients were expected to be already on oxygen treatment before the start of treatment. Details are provided in section 9.1.

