7.1.3 Sensitivity analysis

7.1.3.1 Phase 2

Results of primary analysis will be assessed in sensitivity analyses as detailed below.

- The comparison between treatment and control will be performed by means of a Cox regression model, using age class, gender and clinical severity score at baseline as covariates, to assess the robustness of results on primary endpoint versus the presence of confounding factors. Additional covariates might be included after DRM in case relevant baseline imbalance will be identified between groups, despite randomization. The assumptions of proportionality will be investigated with a time-dependent exploratory variable, which is defined as $\text{treatment} * \{\log[\text{time to event}]\}$. If the p-value from the Wald Chi-squared statistic for this variable is less than 5% there is evidence of a departure from the adjusted model assumptions. In case of non-proportional hazards, a Weibull model will be assumed as parametric form of the distribution of survival times. The treatment group will be included in the model as covariate.
- Time to event for each single component of the primary endpoint will be performed separately in order to adjust for the presence of possible competing risks. The following events:
 - first supplemental oxygen requirement,
 - first mechanical ventilation use,
 - first admission to ICU, and
 - first use of a rescue medication for any reason

will be analyzed according to survival analysis methodology detailed in section 4.1 with the following modifications:

- the common representation of survival curves using the Kaplan-Meier estimator will be replaced by the cumulative incidence function,
- the presence of other competing event(s) is/are treated as censored.
- A modified composite endpoint of phase 2 will be analyzed adding “death” as fifth component. It will be analyzed according to section 7.1.2 to assess the robustness of results on primary endpoint versus the presence of censoring due to fatal events.

Decision to proceed/not proceed to phase 3 will be based only on primary analysis results, despite inconsistencies with sensitivity analyses. Sensitivity results will be interpreted and discussed in the clinical study report and will be used to eventually adjust adaptations for the phase 3.

7.1.3.2 Phase 3

Results of primary analysis will be assessed in sensitivity analyses as detailed below.

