Composite endpoint of phase 2 and Time to event (days)	
From ADDITIONAL INFORMATION form:
 
 • if “Has the patient been admitted to the ICU?” = “Yes”, then component1 = “Yes” and date of event1 = Date of Visit • if “Has the patient been admitted to the ICU?” = “No”, then component1 = “No” 
From PATIENT STATUS form:
 
 • if “Is the subject eligible to switch to rescue medication?” = “Yes”, then component2 = “Yes” and date of event2 = Rescue treatment start date 
 ○ If Rescue treatment start date is missing, then Date of Visit will be used • if “Is the subject eligible to switch to rescue medication?” = “No”, then component2 = “No” 
From ADDITIONAL INFORMATION and MECHANICAL VENTILATION forms:
 
 • If “Has the patient been mechanically ventilated?” = “Yes” and type = “Invasive mechanical ventilation”, then component3 = “Yes” and date of event3 = mechanical ventilation start date 
 ○ If mechanical ventilation start date is missing, then Date of Visit will be used • If “Has the patient been mechanically ventilated?” is not empty and type ≠ “Invasive mechanical ventilation”, then component3 = “No” 
From “Worsening based on PaO₂/FiO₂” (see above):
 
 • if a patient is classified as “Worsened”, then component4 = “Yes” and date of event4 = Date of Visit • if a patient is classified as not “Worsened” (excluding missing classification), then component4 = “No” 
The composite endpoint is equal to “Yes” if at least one post-baseline component (1-4) is equal to “Yes” and the date of event is the corresponding date of event. In case of more component equal to “Yes”, the first date will be used.
 
Otherwise, if all component (1-4) are equal to “No” the composite endpoint will set as “No”. The date of event will be last date where is known that all components are equal to “No”.
 
Time to composite endpoint (days) = Date of event - Date of randomization

Parameter	Derivation

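### The SAP counts only invasive ventilation in both primary composites, where the protocol counts any mechanical ventilation, yet SAP 4.9 says nothing was changed

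*SAP*

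**What the plan says.** Protocol section 3 (Phase 2/3 Study Endpoints) gives the phase 2 composite as "supplemental oxygen requirement, mechanical ventilation use, admission to ICU, and use of a rescue medication for any reason". For phase 3 the event is that "the patient dies or requires mechanical ventilation use and/or admission to ICU". Neither limits ventilation by type, and nor do the protocol summary (section 1) or the analysis sections 9.4.2.1 and 9.4.2.2. The seven-category scale in the same section 3 does separate the types. Category 5 is "hospitalized, requiring high-flow oxygen therapy, noninvasive mechanical ventilation, or both", while invasive ventilation sits with ECMO in category 6.

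SAP 3.5.1 adds one word to each composite. Phase 2 now lists "invasive mechanical ventilation use, admission to ICU, and use of a rescue medication for any reason", and in phase 3 "the subject dies or requires invasive mechanical ventilation use and/or admission to ICU". SAP 9.1, Table 7, puts this into effect. Component 3 is positive only for invasive ventilation, and the negative rule reads, in part, "is not empty and type ≠ “Invasive mechanical ventilation”, then component3 = “No". The same rule appears in all four composite rows: phase 2, modified phase 2, phase 3, and phase 2 by oxygen delivery system.

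SAP 4.9, the section for changes from the protocol, says "No change has been implemented in this SAP". Its one clarification concerns supplemental oxygen. SAP 7.1.3.1 lists the phase 2 component as "first mechanical ventilation use", without the restriction, whereas 7.1.3.2 specifies invasive ventilation for phase 3. SAP 7.2.2.6 reports mechanical ventilation overall and also split into invasive and noninvasive.

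**The concern.** A patient placed on noninvasive ventilation has a primary event under the protocol's plain wording and, on that component, no event under the SAP. This is a change to both primary endpoints, and the section meant to disclose changes denies that there is one.

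Two things depend on it. Phase 2 is the gate: SAP 7.1.3.1 bases the decision to proceed on the primary analysis alone. Also, a reader of the final report would take it from 4.9 that the protocol's endpoint was analysed, and no planned output would show whether the conclusion changes when noninvasive ventilation is counted.

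**Working it through.** **1. Is the definition different?**

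| Place | Ventilation that counts |
|---|---|
| Protocol 1, 3, 9.4.2.1, 9.4.2.2 (both composites) | any type |
| Protocol 3, severity scale | noninvasive named as mechanical ventilation (category 5), invasive in category 6 |
| SAP 3.5.1 (both composites) | invasive only |
| SAP Table 7 (four composite rows) | invasive only |
| SAP 7.1.3.1 (phase 2 component) | type not stated |
| SAP Table 7, time to ventilation use | labelled invasive |
| SAP 7.1.3.2 (phase 3 component) | invasive only |
| SAP 7.2.2.6 (secondary) | both, stratified |

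The protocol's authors had the invasive/noninvasive distinction available on the same page and did not apply it to the endpoints. The SAP therefore narrows them.

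**2. Is the change covered elsewhere?** Protocol 9.4.1 allows endpoints to be modified as an adaptation. SAP Table 6 ties that to the beginning of phase 3 and to a DMC indication from phase 2 results. The narrowing already applies to the phase 2 primary analysis, and 4.9 does not invoke the adaptation.

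**3. Who drops out of the count?**
- Phase 2: a patient on noninvasive ventilation may still count through ICU admission, through rescue (scored from eligibility to switch), or through a fall of at least one third in PaO2/FiO2.
- Phase 3: the only other components are ICU admission and death, so noninvasive ventilation on the ward counts only if intubation, ICU admission or death follows.

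**4. Reproducing the plan's event numbers.** Inputs are SAP 3.2 and Table 2: 2:1 allocation, exponential times and 21 days of follow-up. Medians are 2 vs 5 days in phase 2, and 2 vs 4 to 4 vs 8 days in phase 3. Expected events = Σ n_arm × (1 − 0.5^(21/median)).
- Phase 2: 16 × 0.9993 + 32 × 0.9456 = 46.2 (SAP: 46).
- Phase 3, 2 vs 4 days: 37 × 0.9993 + 74 × 0.9737 = 109.0 (SAP: 109).
- Phase 3, 4 vs 8 days: 37 × 0.9737 + 74 × 0.8379 = 98.0.

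**5. Reproducing the plan's power.** The log-rank drift is √(events × 2/9) × ln(1/HR), with HR 2/5 = 0.4 in phase 2 and 0.5 in phase 3. Simulating the looks with the SAP Table 4 and 5 efficacy and futility bounds gives 80% at 46 events and 90% at 109. These agree with the SAP's approximately 80% for phase 2 and the protocol's 90% for phase 3. (Protocol 9.1's 1.5-fold effect for phase 2 is a separate matter and is not used here.)

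**6. Effect of the narrowing, under an assumption.** The documents do not give the share of patients with noninvasive ventilation only. A patient who loses that trigger stays at risk of the other components, so I lower the event hazard in both arms by a fraction f. I keep the hazard ratio and the information fractions at the interim looks. Follow-up of 21 days then acts as 21(1 − f). Example, phase 2 with f = 20%: 16 × (1 − 0.5^(16.8/2)) + 32 × (1 − 0.5^(16.8/5)) = 15.95 + 28.88 ≈ 44.8.

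| Setting | f | Events | Power | Loss (points) |
|---|---|---|---|---|
| Phase 2, 2 vs 5 days | 0 | 46.2 | 80.3% | – |
| | 10% | 45.6 | 79.8% | 0.5 |
| | 20% | 44.8 | 79.1% | 1.2 |
| | 30% | 43.7 | 78.1% | 2.2 |
| Phase 3, 2 vs 4 days | 0 | 109.0 | 90.3% | – |
| | 20% | 106.9 | 89.7% | 0.6 |
| | 40% | 102.2 | 88.4% | 1.9 |
| Phase 3, 4 vs 8 days | 0 | 98.0 | 87.1% | – |
| | 20% | 91.7 | 84.8% | 2.3 |
| | 40% | 82.0 | 80.6% | 6.4 |

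Every phase 3 row stays above the SAP's stated 80%.

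**The case against.** **The SAP may only be clarifying.** The protocol never formally defines mechanical ventilation, its scale groups the noninvasive form with high-flow oxygen, and the phase 3 composite is meant to capture severe events. Invasive-only is a defensible endpoint. That stands as a reason to keep it, but not as a reason to leave it undeclared: the protocol's own scale uses the term mechanical ventilation for the noninvasive form.

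**Phase 2 is largely covered.** Beyond the rescue and PaO2/FiO2 components, SAP 7.2.2.1 prespecifies a composite in which a move from low flow to BIPAP or CPAP is an event. This stands in part. That composite also counts a move to high-flow nasal cannula without ventilation, and it misses a move from high-flow cannula to BIPAP, because both are in one class. It is not the protocol's composite, and phase 3 has no counterpart.

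**The wording of 7.1.3.1 is shorthand.** A reader might infer that the SAP analyses two different ventilation components. The list is introduced as the components of the primary endpoint, and the Table 7 row for time to ventilation is labelled invasive. This largely stands; what remains is a missing adjective.

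**The trial loses power.** A reader might infer a serious loss by deleting a fixed share of events: 46 to 32 gives 65% in phase 2, and 109 to 65 gives 71% in phase 3. The documents do not support this. They give no such share, and deletion assumes that every affected patient has no other component event by day 21. The footnote to SAP Table 2 also ties the assumed event times to 3.5.1, so the SAP states its targets for the invasive definition.

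**Phase 3 is provisional.** SAP 4.7 requires a protocol amendment and a SAP update before phase 3. That makes correction easy but leaves the phase 2 endpoint and the statement in 4.9 as they are.

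**Conclusion.** The protocol counts any mechanical ventilation in both primary composites, the SAP counts only invasive ventilation, and the statement in SAP 4.9 that nothing was changed is wrong. This rests on the text alone and holds whatever the number of patients affected. No planned analysis in either phase reproduces the protocol's composite. The practical gap is larger in phase 3 than in phase 2.

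The effect on power is unknown. Under the hazard assumption above, with the hazard ratio unchanged, the loss is about 0–2 points in phase 2 and about 1–6 points in phase 3, so no material power loss is claimed.

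A reader might also infer that the endpoint was narrowed after results by arm had been seen. The SAP is dated 29 November 2020, against a protocol of 23 April 2020. The trial is open-label, and 4.9 speaks of enrolled patients in the past tense. The documents give no enrolment dates and no sign that data by arm were consulted, so they support a call for disclosure and nothing further.

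**What to change.** 1. In SAP 4.9, list the restriction to invasive ventilation as a change from the protocol for both primary composites, and give the reason.
2. Add to SAP 7.1.3.1 and 7.1.3.2 a prespecified sensitivity analysis with the same composite and the same Kaplan-Meier and log-rank methods. Component 3 would be positive for mechanical ventilation of any type, dated from its start date. All other components stay as in Table 7, so that only the ventilation term differs.
3. In SAP 7.1.3.1, word the ventilation component to match 3.5.1 and the Table 7 row for time to invasive ventilation.

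This does not require invasive-only to be abandoned as primary; it ensures that both versions are reported. The cost is SAP wording and one extra run per phase. Table 7 already uses the ventilation type and start date, so no new data are needed.

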3.6 Safety endpoints

- Adverse Events (AEs) and Serious Adverse Events (SAEs) throughout the study.
- Safety Laboratory Tests at any available time point;
- Vital signs at any available time point;
- Pregnancy at any available time point.

4. Statistical Analysis

4.1 General

Appropriate descriptive statistics will be produced, according to the variable:

- for continuous data n , mean, standard deviation (SD), median, Q1-Q3, and range (minimum and maximum) will be presented;
- for categorical data, frequency distributions and percentages will be presented;
- for time-to-event variables, cumulative freedom from event will be evaluated using Kaplan-Meier (KM) method. The degree of uncertainty will be expressed with 95% confidence limits (calculated per the method proposed by Greenwood³). Comparison of curves among arms will be performed with the log-rank test. KM graphs will be presented along with the number of subject-at-risk at exact time points. Subjects who have discontinued/terminated the study without an event will be censored at the date of study discontinuation/termination. Subjects ongoing and who are free from event at the time of database lock (for example at interim analyses) will be censored at the last available date.

Unless otherwise specified, hypothesis testing will be carried out at the $\alpha = 0.050$ level (two-sided) when comparing treatments. For all inferential analyses, p-value will be rounded to three decimal places. Statistical significance will be declared if the rounded p-value will be less than or equal to 0.050. For primary analysis only (section 7.1.2), p-values will be provided at 5th decimal place, in order to compare with efficacy and futility thresholds specified in section 4.5.

Additional post-hoc analysis may be produced to further allow comparison between reparixin and control, according to the results obtained. Any unplanned analyses as well as deviations from the original statistical plan will be clearly documented in the Clinical Study Report.

Derivation rules for efficacy and safety analyses are reported in Table 7 in section 9.

All the data collected and derived in the study will be presented in subject data listings by centre.

4.2 Analysis sets

4.2.1 Enrolled set

The Enrolled set (ENR) will consist of all subjects with signed written informed consent and undergoing to study evaluations/procedures.

4.2.2 Randomized set

The Randomized set (RND) will consist of all subjects in the ENR set who are randomized to the study,

regardless of whether they receive the Investigational Medicinal Product (IMP) or not.

4.2.3 Safety set

The Safety set (SAF) will consist of all randomized subjects who receive at least one dose of the IMP. SAF population will be analyzed according to the actual treatment received and will be used to present results on safety data.

4.2.4 Full Analysis set

The Full Analysis Set (FAS) will consist of all randomized subjects who receive at least one dose of the IMP. FAS population will be analyzed according to ITT principle, i.e. by treatment allocation regardless happening of intercurrent events. The FAS population will be used for the primary analyses of the study and to present results on efficacy data.

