#### 6.2 Control treatment

#### Phase 2/3 Control treatment

Control group in both the phase 2 and 3 segments will be standard of care, which due to the nature of the COVID-19 pandemic is expected to evolve over time and, thus, cannot be prespecified. This group will be populated in a prospective manner and offered a rescue medication in case of worsening (e.g. need of ICU and/or mechanical ventilation). Due to the evolving understanding of novel treatments being currently tested during the COVID-19 pandemic, the Sponsor will not put any restriction on the selection of the rescue medication during phase 2. In the phase 3, Reparixin will be offered as rescue medication, as oral tablets or as IV infusion in case of unfeasibility of the oral administration due to the clinical conditions (e.g. intubated patients in the ICU).

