## 6.3 Preparation, Handling, Storage and Accountability of the study drug

#### Study Drug (REPARIXIN tablets)

## FORMULATION

The investigational product is in the form of oral immediate release 600 mg tablets containing the active ingredient reparixin. Reparixin 600 mg immediate release tablets are white oblong tablets.

NAMES OF INGREDIENTS	AMOUNT PER TABLET	FUNCTION OF INGREDIENT	R EFERENCE TO QUALITY STANDARDS
Reparixin (DF 1681Y)	600.0 mg	Drug substance	Internal monograph
Cellulose Microcrystalline	141.48 mg	Diluent/ Disintegrant	Eur. Ph.
Lactose monohydrate	94.77 mg	Diluent	Eur. Ph.
Croscaramellose Sodium	36.00 mg	Disintegrant	Eur. Ph.
Hydroxypropyl cellulose	20.07 mg	Binder	Eur. Ph.

Refer to the following table for Reparixin tablets Description and Composition.

Silica, colloidal anhydrous	3.15 mg	Glidant	Eur. Ph.
Magnesium stearate	4.50 mg	Lubricant	Eur. Ph.
Total	900 mg	-	-

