## 9.3 Analysis Population

The following population will be defined:

• The Safety (SAF) population will consist of all randomized patients who received at least one dose of the investigational product (either Reparixin or Standard of Care). Safety population will be analyzed according to the actual treatment received. The SAF population will be used to present results on safety data.

- The Full Analysis Set (FAS) population will consist of all randomized patients who received at least one dose of the investigational product (either Reparixin or Standard of Care). FAS population will be analyzed according to ITT principle, i.e. by treatment allocation. The FAS population will be used for the primary analyses of the study and to present results on efficacy data.
- The Per Protocol (PP) population will consist of all randomized patients who received at least one dose of the investigational product and do not have Major Protocol Deviations. The PP population will be used for sensitivity analyses.

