4.2.5 Per Protocol set

The Per Protocol set (PP) will consist of all randomized subjects who receive at least one dose of the IMP without any Major Protocol Deviations. The PP set will be used for sensitivity analyses.

All the protocol deviations will be discussed case by case by the clinical team during the Data Review Meeting (DRM) before the database lock and described in the DRM Report.

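### SAP 4.2 defines the full analysis, safety and per-protocol sets by a dose of reparixin, so the place of controls and of never-dosed reparixin patients is not settled, and controls have no stated TEAE start date

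*SAP*

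**What the plan says.** SAP 4.2.4 defines the primary-analysis set: "The Full Analysis Set (FAS) will consist of all randomized subjects who receive at least one dose of the IMP". It adds that "FAS population will be analyzed according to ITT principle, i.e. by treatment allocation regardless happening of intercurrent events". SAP 4.2.3 repeats the condition for safety ("The Safety set (SAF) will consist of all randomized subjects who receive at least one dose of the IMP"), and SAP 4.2.5 limits the per-protocol set to "randomized subjects who receive at least one dose of the IMP without any Major Protocol Deviations".

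Protocol 9.3 words the first two sets differently. A patient qualifies who "received at least one dose of the investigational product (either Reparixin or Standard of Care"). The protocol's per-protocol definition has no such parenthesis. SAP 4.9 states: "No change has been implemented in this SAP".

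On what the product is, protocol 6.3 says "The investigational product is in the form of oral immediate release 600 mg tablets containing the active ingredient reparixin", and protocol 6.2 says "Control group in both the phase 2 and 3 segments will be standard of care". Protocol 6.2 adds that this care will evolve and cannot be fixed in advance.

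SAP 4.2.2 defines a randomized set (RND) regardless of dosing, but SAP Table 3 uses it only for protocol violations, discontinuations and patient status. Efficacy runs on FAS or PP. For adverse events, SAP 8.1 counts an event as treatment-emergent from the first administration of study treatment, and SAP Table 8 uses the IMP start date.

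**The concern.** The set that carries the primary log-rank test cannot be built from the SAP text without a decision that the text does not supply. The protocol wording brings controls back, but leaves open whether a reparixin patient who never took a tablet stays in. In an open-label trial, that should not be decided once allocation and outcomes are known. An exclusion that can apply to only one arm breaks the randomized comparison, and it sits badly with the ITT principle stated in the same SAP section.

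The phase 2 result carries weight. SAP 7.1.3.1 makes the decision to proceed to phase 3 depend on the primary analysis alone. The per-protocol comparison is listed only for phase 3 (SAP 7.1.3.2), and no efficacy analysis uses RND.

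The safety tables have their own gap. With no start date for controls, the programmer's choice decides which control events enter the between-arm tables and which appear only in pre-treatment listings.

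**Working it through.** **1. The plan's own phase 2 figures.** Inputs: 48 patients at 2:1; 46 events; times of 2 and 5 days (SAP Table 2), taken as exponential medians, so the hazard ratio is 2/5 = 0.4; 21 days of follow-up; one-sided 0.025.
- Split: 48 × 2/3 = 32 reparixin, 48 × 1/3 = 16 control.
- Expected events: 16 × (1 − 2^(−21/2)) + 32 × (1 − 2^(−21/5)) = 15.99 + 30.26 = 46.2.
- Fixed-design power (Schoenfeld): Φ(√(46 × 2/3 × 1/3) × ln 2.5 − 1.960) = Φ(2.930 − 1.960) = 83.4%.
- With the SAP Table 4 boundaries at 23 and 46 events: 80.1% if futility is applied, 83.1% if it is ignored.

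The stated 46 events and approximately 80% power are reproduced with all 48 patients in the analysis.

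**2. Who is in the FAS, by reading.**

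| Reading | Reparixin (of 32) | Control (of 16) |
|---|---|---|
| SAP 4.2.4, literal | dosed only | 0, unless given reparixin |
| Protocol 9.3, likely: each arm judged on its own treatment | dosed only | all 16 |
| Protocol 9.3, very literal: either treatment qualifies | all 32, since undosed patients still receive standard of care | all 16 |

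Under the first reading the log-rank information is 46 × 1 × 0 = 0. The SAP clearly does not mean this. SAP 5.4 and 6.1, both run on the safety set, have standard-of-care entries, and SAP 7.1.1 tests reparixin against control. The second and third readings differ only for never-dosed reparixin patients, and neither document chooses between them.

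**3. Direction of a one-arm exclusion.** This is illustrative, because the documents give no number undosed. Assumptions: 32 against 16, no true effect, median 2 days in both arms, events recorded at day 1, 2, 7 or 21, one-sided p < 0.02400, 20,000 simulated trials per case.

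| Reparixin patients excluded | At random | Those with the earliest events |
|---|---|---|
| 0 | 0.026 | 0.026 |
| 1 | 0.025 | 0.035 |
| 2 | 0.026 | 0.049 |
| 3 | 0.026 | 0.068 |

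Exclusion unrelated to outcome does not inflate the error. Inflation appears only when the undosed patients are those who would have failed first. The 0.026 with no exclusion reflects the normal approximation in a small 2:1 sample and is only the reference.

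**4. Cost of keeping undosed patients.** Assumptions: medians 5 and 2 days, undosed patients given the control median, continuous event times, no replacement.

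| Undosed of 32 | Kept | Dropped | Loss against all dosed (0.830) | Loss against dropping |
|---|---|---|---|---|
| 1 | 0.804 | 0.819 | 2.6 points | 1.5 points |
| 2 | 0.784 | 0.820 | 4.6 points | 3.6 points |
| 3 | 0.760 | 0.813 | 7.0 points | 5.3 points |

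Protocol 8.2 allows replacement of active-arm patients withdrawn before completing 24 hours of treatment. If undosed patients are replaced and also kept, power is about 0.82, 0.80 and 0.78. The absolute level depends on the timing assumption: on the day 1, 2, 7, 21 schedule it is about 0.73 rather than 0.83 with nobody undosed.

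**5. Adverse-event clock.** SAP 8.1 and Table 8 each need a start date. Protocol 6.4 records treatments given to controls, but no rule says which of those dates, if any, starts the clock.

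**The case against.** The SAP presents itself as an elaboration of the protocol and declares no change, so a sensible reader would restore the parenthesis for FAS and SAF. A reader might infer from the SAP text that the primary analysis will run without controls. The documents do not support that, since the tables and hypotheses all expect them. Nor was anything dropped for PP, where the protocol has the same gap. Not even every control is literally excluded: phase 2 rescue is unrestricted, and SAP 4.6 foresees crossover subjects. These points stand.

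A reader might also infer that the protocol wording necessarily excludes undosed reparixin patients, or that the type I error is inflated. Neither is established. The one-arm exclusion is the likely reading, not the only one. The number undosed may be zero: drug is dispensed at the randomization visit, naso-gastric dosing is provided for, and exclusion criterion 7 removes patients unfit for oral dosing. Exclusions would be reported with reasons (SAP 5.1) and set membership flagged in listings (SAP 4.3).

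What the objection does not remove is the ambiguity. Disposition counts show who left, not what their leaving did to the result. The missing control date also remains, although the practical gap is probably small, because adverse events are collected from consent and randomization and dispensation share a visit.

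**Conclusion.** The point holds as a defect in stated rules that should be fixed; it is not a demonstrated bias. Three SAP sets carry a condition that controls cannot meet as written. For two of them this departs from protocol 9.3 without being declared. Putting the protocol words back still leaves FAS and SAF membership open for never-dosed reparixin patients. The adverse-event reference date for controls is missing in either case.

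The texts support two workable memberships and one unworkable one, and no planned efficacy analysis would show the difference. The size of any effect on the result is unknown, because it depends on a count that the documents do not give. The simulated rates of 0.035 to 0.068 are a worst case and do not set the importance of the point. That rests on the wording, the open-label design and the role of the phase 2 primary analysis as the sole gate to phase 3.

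**What to change.** 1. Define FAS as all randomized patients, analysed as allocated (the existing RND set). State that patients replaced under protocol 8.2 stay in it, so FAS may exceed 48.
2. Define SAF as all randomized controls plus reparixin patients with at least one dose, by treatment received. List never-dosed reparixin patients separately and do not add them to the control group.
3. Define PP as FAS patients without major protocol deviations, keeping the at-least-one-dose condition for the reparixin arm only. Without that condition, an all-randomized FAS could let undosed reparixin patients into PP.
4. In SAP 8.1 and Table 8, use the randomization date as the TEAE reference for controls, and in both arms for the between-arm comparison. Show the first-dose clock as supplementary for reparixin.
5. Align protocol 9.3 with SAP 4.2 and declare the change in SAP 4.9.

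Controls given reparixin as rescue in phase 3 can be handled in the amendment and SAP update that SAP 4.7 already foresees.

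The cost is wording, with planned enrolment unchanged apart from any replacements that protocol 8.2 already allows. If some reparixin patients are undosed, keeping them dilutes the effect by roughly 2 to 7 points of phase 2 power for 1 to 3 of 32 (continuous times, no replacement), and by less with replacement. If all are dosed there is no cost.
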